### 7.2.2 Per-protocol Population

The per-protocol population consists of all subjects who have measurable lesions at Baseline and no significant protocol deviations determined by the project clinician. The per-protocol population will be used for sensitivity analyses of tumor response.

### 7.2.3 PK Population

The PK analysis population consists of patients with sufficient dosing and PK data to reliably estimate PK parameters as determined by the clinical pharmacologist. The PK population will be used for all PK analyses.

### 7.2.4 Immunogenicity Population

The Immunogenicity population consists of patients who receive at least 1 dose of brentuximab vedotin and have ATA status assessment at Baseline, and at least one postbaseline sample.

## 7.3 Disposition of Subjects

Disposition of patients will be tabulated with the number and percentage of patients for the following categories: patients in each of the study populations in Section 7.2, patients discontinued from the study drug treatment, primary reason to discontinue from the study drug treatment, patients discontinued from the study, and primary reason to discontinue from the study. All percentages will be based on the number of patients in the safety/mITT population.

A listing will be used to present data concerning patient disposition.

### 7.3.1 Protocol Deviations

Protocol deviation will be collected by clinical team and entered into clinical trial management system (CTMS). Important protocol deviation criteria will be established as “Major” in Protocol Deviation and patients with important protocol deviations will be identified and documented before database lock. Important protocol deviations and the number of subjects with important protocol deviations will be tabulated for enrolled patients with HL, with sALCL, and for the combined populations.

#### 7.4 Demographic and Other Baseline Characteristics

Demographic and baseline characteristics will be summarized for patients in the safety/mITT population by disease type. Baseline demographic data to be evaluated will include sex, age, race, ethnicity, body weight, height, and BMI. The formulation for BMI is:

$$\text{BMI} = \frac{\text{weight}(\text{kg})}{\text{height}(\text{m})^2}$$

The following baseline disease characteristics will be summarized for patients in the safety/mITT population by disease type.

At initial diagnosis

- Age at initial diagnosis.
- Evidence of Bone Marrow Involvement.
- Evidence of Extranodal Involvement.
- Ann Arbor Stage.

At Study Entry

- Time since initial diagnosis.
- History of Bone Marrow Involvement.
- Evidence of Extranodal Involvement.
- Ann Arbor Stage.
- B Symptoms.

#### 7.5 Medical History and Concurrent Medical Conditions

A complete medical history will be compiled for each patient during the screening period prior to the first dose of brentuximab vedotin. General medical history of all patients will be presented in a by-patient listing in reported terms.

Concurrent medical conditions that will be assessed include B symptoms (persistent fever, drenching night sweats, and unexplained weight loss >10%) and clinical evaluations of palpable liver and spleen. These assessments will be presented over time in by-patient listings.

B symptom resolution rate is defined as the proportion of patients with lymphoma-related B symptom(s) at baseline who achieve resolution of all B symptoms at any time during the treatment period. For patients with any B symptom at Baseline, B symptom resolution rate and the 95% exact CI will be summarized.

## 7.6 Medication History and Concomitant Medications

Medication history including prior antineoplastic therapy, prior surgery, prior radiation, and prior transplant procedure information that have been received prior to the first dose of brentuximab vedotin, if available, will be presented in by-patient listings. The number and percentage of patients with any prior event will be tabulated by disease type based on the safety/mITT population. The best response to last prior therapy will also be tabulated by disease type. For ordering purposes, prior therapies with partial end date will have the date imputed as the last day of the month or December 31st if the month is also unknown, but no later than the date of first dose of study drug. All dates presented in listings are recorded dates without imputation.

Concomitant medication is defined as any medication administered between the first dose of the study drug and the EOT visit. Concomitant medications will be coded by preferred term using the World Health Organization (WHO) Drug Dictionary (March 2012 Version or higher). The number and percentage of patients taking concomitant medications will be tabulated by Anatomical Therapeutic Chemical (ATC) classification pharmacological subgroup and WHO drug generic term. Patients are counted once for each ATC pharmacological subgroup and once for each WHO generic term.

Subsequent anticancer therapies received after EOT will be tabulated separately.

Concomitant procedures will not be coded, instead will be presented in a by-patient listing.

## 7.7 Study Drug Exposure and Compliance

The exposure to brentuximab vedotin will be characterized by total amount of dose taken (mg), number of treated cycles, duration of treatment (days), and relative dose intensity (RDI, %).

Total amount of dose taken (mg) is the summation of actual doses (prepared dose (mg) × (actual volume / prepared volume)). Total dose expected (mg) is the summation of expected doses (dose level initially assigned multiply by weight used for dosing calculation). Dose intensity (mg/kg/week) is total dose (mg/kg) / (duration of treatment in days /7). Relative dose intensity (RDI) is

$$\text{RDI (\%)} = \frac{\text{Dose intensity (mg/kg/week)}}{\frac{\text{expected dose level (1.8 mg/kg)}}{\text{Number of treated cycles} \times 3}} \times 100\%$$

A treated cycle is defined as a 21-day period, during which the patient receives any amount of brentuximab vedotin (scheduled for single dose in 21-day period). The duration of treatment is defined as time from the first study dose to 21 days after the last study dose, or death date, whichever is earlier:

$$\text{Duration of treatment} = \min(\text{Last dose date} + 21, \text{death}) - \text{First dose date}$$

Action on study drug (including dose reduced, increased, missed, delayed, interrupted, held, or discontinued permanently) will be summarized by Cycle 1 through 16. Percentage will be calculated based on the number of patients treated during each cycle.

Dosing data including dose modification and action on drug will also be presented in a by-patient, by-cycle listing.

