#### **14.1.7 Safety Analysis**

Safety will be evaluated by the incidence of AEs, severity and type of AEs, and by changes from Baseline in the patient's vital signs and clinical laboratory results using the safety population. Exposure to study drug, including the number of treated cycles, total amount of doses taken, and dose intensity will be summarized.

TEAEs that occur after administration of the first dose of study drug and through 30 days after the last dose of study drug will be tabulated. A listing of deaths and TEAEs resulting in study drug discontinuation will be provided.

AEs will be tabulated according to the MedDRA and will include the following categories:

- TEAEs.
- Drug-related TEAEs.
- Grade 3 or higher TEAEs.
- Grade 3 or higher drug-related TEAEs.
- SAEs.

Descriptive statistics for the actual values of clinical laboratory parameters (and/or change from Baseline in clinical laboratory parameters) will be presented for all scheduled measurements over time. Mean laboratory values over time will be plotted for key laboratory parameters. Shift tables for laboratory parameters will be generated based on changes in NCI CTCAE grade from Baseline to the worst post-Baseline value. Graphical displays of key safety parameters, such as scatter plots of Baseline versus worst post-Baseline values, may be used to understand the brentuximab vedotin safety profile.

Descriptive statistics for the actual values (and/or the changes from Baseline) of vital signs (eg, blood pressure, pulse rate, and axillary temperatures) and weight over time will be tabulated by scheduled time point. ECOG performance status scores over time will also be tabulated.

Additional safety analyses may be performed to most clearly enumerate rates of toxicities and to further define the safety profile of brentuximab vedotin.

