### 4.4 Study Design

This is a single-arm, open-label, multicenter, phase 2 study designed to evaluate the efficacy, safety, and PK of brentuximab vedotin as a single agent in Chinese patients with relapsed/refractory CD30+ HL or sALCL. Brentuximab vedotin will be administered as a single, 1.8 mg/kg IV infusion on Day 1 of each 3-week cycle.

Patients will receive a maximum of 16 cycles if they do not meet the criteria for removal from the study. Patients will be assessed for overall response using the Revised Response Criteria for Malignant Lymphoma [1]. Dedicated computed tomography (CT) scans (neck, chest, abdomen, and pelvis) will be performed at Baseline and at Cycles 2, 4, 7, 10, 13, and 16, and positron emission tomography (PET) scans will be performed at Baseline and at Cycles 4 and 7. No additional PET scanning is required beyond Cycle 7 unless clinically indicated. B symptoms will be assessed at Baseline and on Day 1 of each cycle.

Patients may continue on study treatment until the sooner of disease progression, unacceptable toxicity, or completion of 16 cycles. Patients, including those who discontinue study treatment for any reason other than withdrawal of consent, will have safety follow-up assessments through 30 days after the last dose of study drug until end of treatment (EOT). Patients who discontinue study treatment with stable disease (SD) or better will be followed for PFS until disease progression, death, withdrawal of consent, or initiation of a new treatment other than the stem cell transplantation (SCT), whichever occurs first. A CT scan will be performed every 12 weeks for the first 12 months and at 18 months after EOT. Patients will be followed for OS every 12 weeks until death, withdrawal of consent, or study closure, whichever occurs first. All patients will have the opportunity to be followed for 18 months after EOT. The study will be closed when all patients enrolled have completed the required follow-up.

Toxicity will be evaluated according to the National Cancer Institute Common Terminology Criteria for Adverse Events (NCI CTCAE), version 4.03, effective 14 June 2010 [2]. Laboratory values, vital signs, and electrocardiograms (ECGs) will be obtained to evaluate the safety and tolerability of brentuximab vedotin. Serial blood samples for determination of the serum/plasma

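### SAP 7.7: the relative dose intensity formula, as printed, returns the true value multiplied by the number of treated cycles (1600% for perfect dosing over 16 cycles)

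*SAP*

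**What the plan says.** SAP 7.7 (Study Drug Exposure and Compliance) characterizes exposure by four measures: total dose in mg, number of cycles, duration of treatment, and RDI in percent. It builds RDI as follows.

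- **Numerator.** "Dose intensity (mg/kg/week) is total dose (mg/kg) / (duration of treatment in days /7). Relative dose intensity (RDI) is" followed by a displayed equation with dose intensity on top.
- **Denominator.** A nested fraction: the expected dose level of 1.8 mg/kg over the "number of treated cycles" times 3.
- **Duration.** "time from the first study dose to 21 days after the last study dose, or death date, whichever is earlier".
- **A quantity that is defined but not used.** "Total dose expected (mg) is the summation of expected doses". It does not appear in the RDI equation.

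The planned regimen is in SAP 4.4: "Brentuximab vedotin will be administered as a single, 1.8 mg/kg IV infusion on Day 1 of each 3-week cycle", and "Patients will receive a maximum of 16 cycles if they do not meet the criteria for removal from the study".

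Protocol 14.1.7 asks only for dose intensity and gives no RDI formula: "Exposure to study drug, including the number of treated cycles, total amount of doses taken, and dose intensity will be summarized". Apart from the abbreviation list, RDI appears nowhere else in either document.

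**The concern.** RDI should compare the dose rate delivered with the dose rate planned, so that full dosing on schedule scores 100% however long treatment lasts. Here the numerator is already a rate per week over all cycles. The denominator takes one dose and divides it by the weeks of all cycles. The planned dose was not multiplied by the number of cycles, so the two sides do not match.

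If the formula is programmed as written, RDI mixes how well the dose was delivered with how long the patient stayed on treatment. Patients with different numbers of cycles cannot be compared. Nor can the HL and sALCL groups, which SAP 7.1 summarizes separately, if their treatment lengths differ. A mean or median would mostly reflect cycles received. Safety is a co-primary endpoint, and readers need exposure to interpret toxicity. Among the four measures listed in SAP 7.7, RDI is the only one that carries dose intensity.

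**Working it through.** The plan states no numerical RDI, so there is no figure to reproduce. The check evaluates the formulas directly.

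**Inputs.** Planned dose 1.8 mg/kg every 3 weeks, maximum 16 cycles (SAP 4.4). Dose intensity, duration and RDI formulas from SAP 7.7. A reduction to 1.2 mg/kg and delays of up to 3 weeks are both provided for in Protocol 9.2. Total dose in mg/kg is read as cumulative.

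**Formulas.** Let N be the number of treated cycles and DI the dose intensity.

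- DI = total mg/kg ÷ weeks on treatment
- Printed RDI = DI ÷ [1.8 / (3N)] × 100
- RDI against planned intensity = DI ÷ [1.8 / 3] × 100
- Ratio of the two = (1.8/3) ÷ [1.8/(3N)] = N

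The ratio is N for any dosing history. Delays, reductions and the cut-off at death change DI, but DI enters both versions in the same way.

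**On-time, full-dose patient.** Duration is 21N days, or 3N weeks, so DI = 1.8N / 3N = 0.6 mg/kg/week for every N. The printed denominator is 0.6/N, which gives 100% × N.

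**Illustrative histories**

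| History | N | Weeks | Total mg/kg | DI | Printed RDI | Against 0.6/week |
|---|---|---|---|---|---|---|
| Full, on time | 1 | 3 | 1.8 | 0.600 | 100% | 100% |
| Full, on time | 2 | 6 | 3.6 | 0.600 | 200% | 100% |
| Full, on time | 4 | 12 | 7.2 | 0.600 | 400% | 100% |
| Full, on time | 8 | 24 | 14.4 | 0.600 | 800% | 100% |
| Full, on time | 16 | 48 | 28.8 | 0.600 | 1600% | 100% |
| On time, 8 of 16 doses at 1.2 mg/kg | 16 | 48 | 24.0 | 0.500 | 1333% | 83.3% |
| Full, one 3-week delay | 16 | 51 | 28.8 | 0.565 | 1506% | 94.1% |
| Second dose 1.2 mg/kg, 3 weeks late | 2 | 9 | 3.0 | 0.333 | 111% | 55.6% |
| One full dose, death 7 days later | 1 | 1 | 1.8 | 1.800 | 300% | 300% |

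Three things follow.

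- Rankings can reverse. The patient with 4 perfect cycles prints 400%, below the 1333% of the patient with eight reduced doses, although the true values are 100% and 83.3%.
- A wrong value can look acceptable, as in the 111% row.
- The two versions agree only at N = 1.

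**Could the layout explain it?** N appears once in the equation, while DI for on-time dosing does not depend on N. No regrouping of the printed terms can therefore give 100% at every N. Reading the denominator as (1.8/N) × 3, for example, gives 0.6 ÷ 0.3375 = 178% at N = 16. Only a missing term, such as a factor N beside 1.8 mg/kg, would repair it.

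**The case against.** Four points can be made on the other side.

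1. **Extraction.** The equation was read from a PDF by a program, and a multiplier in the upper term could have been lost. The unused cumulative expected dose fits a lost term as well as it fits a drafting slip. This stands as a caveat: the conclusion concerns the formula as it reads, and the source PDF should be checked first.

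2. **Meaning of total dose.** SAP 7.7 does not say how the total in mg becomes a total in mg/kg. If that term meant the average dose per cycle, the printed formula would equal (mean dose / 1.8) × (3N / weeks), which is correct. But the section speaks of a total and a summation. The averaged reading would also make dose intensity itself wrong: perfect dosing over 16 cycles would have an intensity of 1.8/48 = 0.0375 mg/kg/week instead of 0.6. The cumulative reading is an assumption, but a safe one.

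3. **Importance.** RDI is descriptive and supports no decision. Dosing listings by patient and cycle are planned, so the correct value could be recovered. A result of 1600% would be hard to miss, and the 111% case is a constructed history whose frequency the documents do not give. All of this is true and limits the severity. It does not make the formula right, and a programmer who corrects it silently would depart from the SAP.

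4. **Death.** The duration rule already covers early death, so the 300% in the last row follows from a stated rule and has nothing to do with the factor N. This is accepted. Handling of early death is an optional clarification and no part of the error.

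**Conclusion.** The concern holds. As printed, RDI in SAP 7.7 equals the true relative dose intensity times the number of treated cycles, an inflation between 1-fold and 16-fold under the 16-cycle maximum. This rests on the equation having been extracted faithfully and on total dose being cumulative.

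The error is confined to this one measure. The formulas for dose intensity, total dose, number of cycles and duration are sound, and nothing else in either document uses RDI. The overall response rate and its confidence intervals, the adverse event tables and the sample size do not change. It should be corrected before the exposure tables are programmed, but it does not threaten the trial's conclusions.

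**What to change.** After checking the source PDF, replace the denominator with the planned intensity:

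RDI (%) = dose intensity (mg/kg/week) ÷ (1.8 mg/kg / 3 weeks) × 100

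An equivalent denominator is (1.8 × treated cycles) / (treated cycles × 3). Either gives 100% for full, on-time dosing at any number of cycles.

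Two sentences would be useful but are optional. One would say how actual doses in mg are converted to mg/kg, for example by dividing each dose by the weight used to calculate it. The other would say how values above 100% that arise only because death shortened the duration are to be presented.

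The cost is one formula in the SAP, up to two clarifying sentences, and one derivation in the program. No new data are needed and no endpoint changes.

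### Cutting treatment duration at death biases relative dose intensity upward for patients who die within 21 days of their last dose

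*SAP*

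**What the plan says.** SAP 7.7 (Study Drug Exposure and Compliance) builds RDI from four definitions.

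- Dose: "Total amount of dose taken (mg) is the summation of actual doses". Nothing is taken off the last dose if the patient dies before the cycle ends.
- Time: "The duration of treatment is defined as time from the first study dose to 21 days after the last study dose, or death date", taking the earlier of the two. The formula given is min(last dose date + 21, death) − first dose date.
- Observed rate: "Dose intensity (mg/kg/week) is total dose (mg/kg) / (duration of treatment in days /7").
- Expected rate, the RDI denominator: "expected dose level (1.8 mg/kg") divided by three times the "number of treated cycles". A cycle is a fixed length: "A treated cycle is defined as a 21-day period, during which the patient receives any amount of brentuximab vedotin".

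SAP 4.4 caps treatment: "Patients will receive a maximum of 16 cycles". SAP 7.1 summarises continuous variables by mean, standard deviation, median, minimum and maximum, for HL, for sALCL and for all patients. Protocol 14.1.7 lists dose intensity among the exposure summaries in the safety analysis.

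**The concern.** The two halves of the ratio run on different clocks. The expected rate gives the last cycle its full 21 days. The observed rate gives that cycle only the days up to death, yet credits the whole dose to it. A patient who received exactly the planned doses on the planned days therefore scores above 100% only because of dying before the cycle ended.

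RDI is meant to show how far delays and reductions took patients below plan, and safety is a primary endpoint. In a cohort of about 8, one inflated value can move the mean by an amount comparable to the departures RDI is meant to reveal. Protocol 4.1.4 notes that deaths within 30 days of the last dose were relatively more frequent in sALCL than in HL in the earlier phase 2 studies, so the smaller cohort is the likelier place for it to happen.

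**Working it through.** **Inputs.** Planned dose 1.8 mg/kg once per 21-day cycle, and the duration, dose-intensity and RDI rules, all from SAP 7.7; maximum 16 cycles from SAP 4.4. Total dose in mg/kg is taken as the sum of the mg/kg doses given. The interval from last dose to death, d days, is not in the documents; it is assumed over 7 to 20 days. The SAP states no RDI value to reproduce, so the reference is a patient with full doses on schedule who does not die. That patient should score 100%.

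**Reference patient, n cycles.** Duration = 21(n − 1) + 21 = 21n days. Dose intensity = 1.8n / (21n/7) = 0.6 mg/kg/week.

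- Against 0.6 mg/kg/week (1.8 mg/kg per 3 weeks): 100% for every n.
- Against the denominator as printed, 1.8/(3n): 0.6 × 3n/1.8 = n × 100%, that is 100% for 1 cycle, 200% for 2, 400% for 4 and 1600% for 16. The printed expression does not multiply the dose by the number of cycles. This is a separate and larger defect in the same formula. The working below uses 0.6 so that the effect of death is seen alone.

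**Death d days after the last dose, d < 21.** Duration = 21(n − 1) + d. Dose intensity = 1.8n × 7 / (21(n − 1) + d). Dividing by 0.6:

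RDI = 21n / (21(n − 1) + d)

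| Cycles n | d = 7 | d = 10 | d = 14 | d = 20 |
|---|---|---|---|---|
| 1 | 300% | 210% | 150% | 105% |
| 2 | 150% | 135.5% | 120% | 102.4% |
| 3 | 128.6% | 121.2% | 112.5% | 101.6% |
| 4 | 120% | 115.1% | 109.1% | 101.2% |
| 8 | 109.1% | 107.0% | 104.3% | 100.6% |
| 16 | 104.3% | 103.4% | 102.1% | 100.3% |

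For example, n = 2 and d = 7 gives 42/28 = 150%. At d = 7 the value exceeds 120% only for 1 to 3 cycles. With n = 1 the printed denominator is already 1.8/3 = 0.6, so the 300% arises from the formula exactly as printed. Death on the day of the first dose gives a duration of 0 and an undefined RDI, for which SAP 7.7 has no rule.

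**Delays and reductions.** With a total delay of D days, RDI = 21n / (21(n − 1) + D + d).

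- n = 2, d = 10, D = 11: 42/42 = 100%.
- n = 2, d = 10, D = 14: 42/45 = 93.3%. Without the cut at death the same dosing gives 42/56 = 75%.
- 1.2 mg/kg throughout, n = 4, d = 7: (4 × 1.2)/(70/7) = 0.48, and 0.48/0.6 = 80%. Without the cut, 4.8/(84/7) = 0.40, and 0.40/0.6 = 66.7%.

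The value can fall to or below 100%, but it stays above what the same dosing gives without the cut.

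**Effect on a mean of 8 (illustration).** One patient at 300% instead of 100% moves the mean by 200/8 = 25 points; one at 150% moves it by 50/8 = 6.25 points. With one value of 300% and seven at 95%, the mean is (300 + 665)/8 = 120.6%, while the median stays at 95%.

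**The case against.** Ending treatment duration at death is a natural definition, since nobody is on treatment afterwards. That stands for duration as a descriptive variable. It does not justify using that duration as the time base of a ratio whose other half counts whole cycles.

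The practical harm is limited, and this also stands. SAP 7.7 tabulates dose actions by cycle and lists dosing by patient and cycle. The median resists a single extreme value, the maximum would expose it, and SAP 7.11.1.3 lists all deaths. RDI enters neither the response rate nor the sample size.

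A reader might infer that anyone who dies within 21 days of any dose scores well above 100%. The definitions do not support that: only the interval after the last dose matters, the excess shrinks as cycles accumulate, and delays or reductions can cancel it. A reader might also take a mean near 121% in sALCL as a forecast. It needs one patient in eight to die 7 days after a single dose. Protocol 4.1.4 gives no count of such deaths, and Protocol 8.1 requires an ECOG status of 0 or 1 and expected survival of at least 3 months.

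Finally, the printed denominator distorts RDI more, and for every patient with 2 or more cycles. That is a reason to make both corrections together. It does not dispose of this one, which remains after the denominator is put right.

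**Conclusion.** The point holds as a minor error in a derived exposure variable. Under SAP 7.7, death within 21 days of the last dose always raises RDI above what the same dosing would otherwise give. For full doses on schedule against 0.6 mg/kg/week, the excess runs from large after 1 to 3 cycles when death comes soon after the dose, to a few percentage points or less by 16 cycles. These figures rest on assumed days of death; how many patients would be affected cannot be judged from the documents. Masking of delays and reductions elsewhere in the cohort is a risk for the mean only, because the other planned summaries would show them. Efficacy conclusions are not affected.

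**What to change.** In SAP 7.7, define the time base for dose intensity and RDI as last dose date + 21 − first dose date, without the cut at death. Keep the truncated quantity as the descriptive duration of treatment. In the same edit, write the RDI denominator as 1.8 mg/kg per 3 weeks, that is 0.6 mg/kg/week.

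Both edits are needed. Removing the cut alone leaves n × 100% under the printed denominator; correcting the denominator alone leaves the values in the table. With both, every fully dosed, on-schedule patient scores 100%, whether or not death follows, and the zero-duration case disappears.

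The cost is one further line in the SAP and a second duration variable, which counts nominal days after death and should be labelled as such. Data collection, dosing and the efficacy analyses do not change.
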